3.14. Prior/Concomitant Medications and Procedures

The start and stop date, dose, unit, frequency, route of administration, and indication for all prior medications (taken within the 90 days prior to the Screening Visit) will be recorded. All prior EN3835, CCH, XIAFLEX® and QWO (CCH-aaes) use should be recorded.

The start and stop date, dose, unit, frequency, route of administration, and indication for all concomitant (taken from the Baseline Visit through the Day 180 Visit) medications and nondrug therapies (eg, blood transfusions, oxygen supplementation, physical therapy, etc) received will be recorded.

3.14.1. Prohibited Medications/ Procedures

During the study, the following treatments are prohibited:

- Antiplatelet medication, such as (clopidogrel [Plavix®], including aspirin) at any dose within 14 days of treatment.
- Anticoagulants, such as warfarin (Coumadin®); heparin analogues, or Factor Xa inhibitors, within 14 days of treatment.
- NSAIDs, such as ibuprofen (Motrin®, Advil®) and naproxen (Aleve®), 7 days before the study.
- Any medications (eg, corticosteroids, certain antidepressants [eg, citalopram, fluoxetine], nutritional/homeopathic supplements [eg, fish oil, Vitamin E, omega 3, gingko biloba, ginger, St John's Wart, green tea, ginseng, feverfew, saw palmetto, turmeric, bromelain]) or foods (eg, pineapple) that have, or have been reported to have anticoagulant effects within 14 days of treatment.
- Tranexamic acid within 30 days before treatment.
- For participants allocated to Cohort 5, drugs associated with methemoglobinemia
- For participants allocated to Cohort 7, combination hormonal contraceptives and hormonal therapy received during the study.

During the study, the following procedures are prohibited in the buttocks:

• Liposuction during the 12-month period before dosing with study intervention.

- Injections radiofrequency device treatments; laser treatment; buttock implant treatment; cryolipolysis or surgery during the 12-month period before injection of study intervention.
- Any investigational treatment for cellulite during the 12-month period before the injection of study intervention.
- Endermologie or similar treatments during the 6-month period before injection of study intervention.
- Creams (eg, Celluvera[™], TriLastin[®]) and/or home therapies to prevent or mitigate cellulite during the 2-week period before injection of study intervention.

If a prohibited medication or procedure is used during the study, all pertinent information will be recorded. The Sponsor must be informed to determine whether the participant can continue in the study.

3.14.2. Permitted Concomitant Medications

During the study, acetaminophen will be permitted to treat pain at the injection site as needed. Other required concomitant medications may be administered at the investigator's discretion.

3.15. Adverse Events and Serious Adverse Events

All AEs and SAEs will be collected by the investigator from the time of signing the informed consent through the Day 180/EOS/ET Visit.

All AEs, including both observed or volunteered problems, complaints, signs or symptoms must be recorded, regardless of whether associated with the use of study intervention. Study intervention includes QWO (CCH-aaes) at the labeled dose and at different strengths (concentrations), diluent additives, depths, and method of injection. This would include AEs resulting from concurrent illness, reactions to concurrent medication use, or progression of disease states (excluding the disease under study). A condition present at baseline that worsens after initiation of study intervention will be captured as an AE, the onset date will be the date the event worsened.

3.15.1. Adverse Events (AE)

An AE is any unfavorable or unintended change in body structure (signs), body function (symptoms), laboratory result (eg, chemistry, X-ray, etc), or worsening of a preexisting condition associated temporally with the use of the study intervention whether or not considered related to the study intervention. Note: Any medical condition or laboratory abnormality already present at screening or baseline should be reported as medical history. If the medical condition present at baseline changes in severity or seriousness at any time during the study, it should be reported as an AE. AEs will be captured once a participant has signed the informed consent. AEs include:

- Changes in the general condition of the participant.
- Subjective symptoms offered by or elicited from the participant.
- Objective signs observed by the investigator or other study personnel.

- All concurrent diseases and/or medical occurrences that occur after the start of the study, including any change in severity or frequency of pre-existing disease.
- All clinically relevant laboratory abnormalities or physical findings that occur during the study.

3.15.2. Serious Adverse Events (SAE)

An SAE is defined as an AE that:

- Results in death.
- Is immediately life-threatening (there is an immediate risk of death from the AE as it occurred; this does not include an AE that had it occurred in a more serious form may have caused death).
- Results in or prolongs an inpatient hospitalization (Note: a hospitalization for elective or preplanned surgery, procedure, or drug therapy does not constitute an SAE).
- Results in permanent or substantial disability (permanent or substantial disruption of one's ability to conduct normal life functions).
- Is a congenital anomaly/birth defect (in offspring of a participant using the study intervention regardless of time to diagnosis).
- Is considered an important medical event.

Important medical events are defined as events that, based upon appropriate medical judgment, may jeopardize the participant and may require medical or surgical intervention to prevent one of the other serious outcomes. Examples of important medical events include any cancer, allergic bronchospasm requiring intensive treatment in an emergency room or at home, blood dyscrasias or convulsions that do not result in inpatient hospitalization, or the development of drug dependency or drug abuse.

For more details on the time period, frequency, methods of collection of adverse events, etc. please refer to protocol section 9.4.

3.16. Safety Assessments

All safety assessments will be performed at the time points outlined in the SoA (Table 3, Table 4, Table 5, and Table 6). Additional (unscheduled) safety assessments may be performed as needed.

3.16.1. Vital Signs

Vital signs (temperature, pulse, systolic and diastolic blood pressures) will be collected for Cohort 1-5 on Screening, Day 1, Day 22, Day 43 and Day 180/EOS/ET, for Cohort 6 on Screening, Day 1, Day 43 and Day 180/EOS/ET and for Cohort 7 on Screening, Day 1, Day 22, Day 43, Day 64 and Day 180/EOS/ET. For treatment visits, ie, on Day 1, Day 22 and Day 43 for Cohort 1-5; Day 1 and Day 43 for Cohort 6 and Day1, Day 22, Day 43 and Day 64 for Cohort 7, the vital signs will be collected up to 2 hours prior to, and at 15 and 30 minutes after, QWO (CCH-aaes) administration. Pulse and blood pressure will be collected after the participant has

been sitting for 5 minutes. Any vital sign value meeting the investigator's criteria for clinical significance will be recorded as an AE (or SAE, if appropriate).

3.16.2. Pregnancy Testing

All female participants of childbearing potential will have serum and/or urine pregnancy tests at the time points outlined in the SoA (Table 3, Table 4, Table 5, and Table 6). Results must be available prior to QWO (CCH-aaes) administration. Participants with positive results at the Screening Visit or on Day 1 will be ineligible for study entry. Any female participant that becomes pregnant during the study will be withdrawn from the study.

For all female participant of childbearing potential, the participant's agreement to use contraception throughout their study participation (Screening Visit through the Day 180/EOS/ET Visit, or for a minimum of 28 days after the last dose of study intervention for participants who terminate early) will be documented.

3.16.3. Clinical Laboratory Determinations

At the time points listed in the SoA (Table 3, Table 4, Table 5, and Table 6), clinical laboratory tests will be conducted. Required clinical laboratory tests are outlined in Table 12.

Samples for laboratory testing may be collected under fasted or nonfasted conditions. Fasting early morning samples are preferred, but a random daytime sample is acceptable. The date and time of the sample collection must be documented in the laboratory report. Investigators must review and sign laboratory reports and document the clinical significance of each laboratory abnormality. New clinically significant laboratory abnormalities or clinically significant changes in laboratory values will be reported as AEs (or SAEs, if appropriate).

Table 12: Clinically Important Laboratory Parameters

Hematology	Biochemistry	Urinalysis
Hemoglobin	Glucose	Glucose
Hematocrit	Sodium	Protein
Red blood cell (RBC) count	Potassium	Specific gravity
Platelets	Calcium	рН
White blood cell (WBC) count	Chloride	Ketones
WBC Differential	Carbon dioxide (CO ₂)	Bilirubin
Prothrombin time (PT)/	Blood urea nitrogen (BUN)	Urobilinogen
International Normalized Ratio	Creatinine	Nitrite
(INR)	Aspartate aminotransferase (AST)	Blood ^a
	Alanine aminotransferase (ALT)	Leukocytes ^a
	Gamma-glutamyl transferase (GGT)	
	Total bilirubin (direct bilirubin reflex if elevated)	
	Albumin	
	Alkaline phosphatase (ALP)	
	Total protein	

^{a.} Microscopic examination will be performed if blood or leukocytes are detected

4. STUDY PARAMETERS

4.1. Participant Disposition

A participant will be considered to have completed the study if they complete the Day 180/EOS Visit. Any participant terminating early from the study before the end of the study is said to be ET.

If a participant withdraws from the study, all EOS/ET procedures should be conducted as detailed in the SoA (Table 3, Table 4, Table 5, and Table 6). The reason and date for discontinuation will be recorded in the eCRF for participants who do not complete the study. If, however, a participant withdraws consent, no additional procedures are required except the collection of AE information at the Safety Follow-up Visit, 28 days after the last treatment. This information should be recorded in the source documentation and the eCRF.

4.2. Demographics and Baseline Characteristics

Demographics and baseline characteristics will include following parameters:

Table 13: Demographic and Baseline Characteristics

Continuous Variables	Categorical Variables		
Age (years)	Gender		
Height (cm)	Race		
Weight (kg)	Ethnicity		
BMI (kg/m²)	Skin category based on Fitzpatrick scale assessment		
Time since last menstrual period (days)	Substance Use		
	Alcohol use (Never, Current and Former)		
	Tobacco use (Never, Current and Former)		
	Hexsel CSS scores		
	CR-PCSS Score		
	IABSS Ratings at Visit 1 (Day 1)		
	Cellulite History		

4.3. COVID-19 Related Protocol Deviations

All study assessments conducted outside of the allowed windows outlined in the SoA (Table 3, Table 4, Table 5, and Table 6) due to a COVID-19 interruption will be documented as a protocol deviation.

COVID-19 will be recorded as the reason for these out-of-window assessments.

4.4. Prior/Concomitant Medications and Procedures

All medications will be coded using World Health Organization (WHO) Drug Dictionary Version Global B3 March, 2022, by active ingredient and WHO anatomical therapeutic chemical (ATC) classification of ingredients.

• A prior medication/procedure is defined as any medication/procedure taken/done prior to first injection (Day 1).

• A concomitant medication (or non-drug therapy) is any medication (or therapy) taken on or after the Baseline Visit through the Day 180/EOS/ET Visit or the medication is reported as ongoing.

[figure not shown]
Please note that if a medication star.ted prior to Screening and end date is after screening/ongoing, it will be counted as both prior and concomitant medication.

4.5. Efficacy Parameters

4.5.1. IABSS Ratings

The IABSS rating is directly obtained from the investigator's assessments at treatment visits and their corresponding follow-up visits, ie, Visit 1 (Day 1) through Visit 15 (Day 57) for Cohorts 1-5, Visit 1 (Day 1) through Visit 11 (Day 57) for Cohort 6, and Visit 1 (Day 1) through Visit 20 (Day 78) for Cohort 7.

For the primary and secondary analysis, the following definition will be used for Cohorts 1 to 7 for the primary endpoint: A one-level IABSS responder at Visit A versus Visit B is defined as the participant whose left buttock (investigational side) at Visit A demonstrates at least a 1-level lower IABSS score versus the right buttock (control side) at Visit B, where Visit A and B can either be same or different.

4.5.2. I-GAIS Ratings

The I-GAIS ratings are directly obtained from the investigator's assessment at Visit 6 (Day 22), Visit 11 (Day 43), Visit 16 (Day 90), Visit 17 (Day 135) and Visit 18 (Day 180) for Cohort 1-5. For Cohort 6, the I-GAIS ratings will be obtained at Visit 7 (Day 43), Visit 12 (Day 90), Visit 13 (Day 135) and Visit 14 (Day 180) and for Cohort 7, at Visit 6 (Day 22), Visit 11 (Day 43), Visit 16 (Day 64), Visit 21 (Day 90), Visit 22 (Day 135) and Visit 23 (Day 180).

A one-level I-GAIS responder for a treatment area (left buttock or right buttock) is defined as any participant with an improved (+1, +2 or +3) score on the I-GAIS at an analysis visit for that treatment area.

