Support for the use of more dilute concentrations of QWO (CCH-aaes) is derived from Studies EN3835-209 and EN3835-224 (see Section 3.3.3). Support for half-dose and quarter-dose of QWO (CCH-aaes) is derived from Study AUX-CC-831 (see Section 3.3.5). Study AUX-CC-831 tested QWO (CCH-aaes) at 0.06 mg, 0.48 mg, and 0.84 mg. The study demonstrated improvement in a variety of parameters with the 0.06 mg dose, and investigators determined that approximately 45% of participants had improvement in their cellulite, although it was not statistically significant. The 0.48 mg dose was associated with statistically significant improvements. Therefore, in this study, Cohort 6 will evaluate a QWO (CCH-aaes) dose between the lowest and the middle dose given in Study AUX-CC-831, to determine whether there will be a decrease in bruising while experiencing an improvement in cellulite.

Administering QWO (CCH-aaes) using a shallower depth of injection (¼ inch) rather than the labeled depth (½ inch) injection is supported by the results of a study conducted by Whipple et al (2021). Using ultrasound, the investigators identified the depth of the fibrous septa causing cellulite and delineated their anatomical orientation. The average skin thickness in 92 buttock dimples was 0.28 cm and the depth of superficial fascia was 0.84 cm. A depth of a ¼-inch

(0.64-cm) injection would place the tip of the needle within the superficial subcutaneous tissue. The majority of fascial bands originate from the superficial fascia and therefore using a shallower depth of injection could facilitate the lysis of the causative bands while potentially avoiding more expanded vasculature when using a deeper injection. This approach is further supported by the method used in a subcision technique for cellulite, which uses a depth of 0.06 cm to 0.10 cm (Green and Cohen, 2015).

In Study EN3835-224, a more dilute concentration of QWO (CCH-aaes) was used to treat cellulite. In this study's 2-aliquot cohort, a concentration of QWO (CCH-aaes) 0.05 mg/mL, combined with injecting QWO (CCH-aaes) at ¼-inch and ½-inch depths, was demonstrated to be safe and well-tolerated with a low incidence of discoloration. In this study (APHRODITE-1), Cohorts 2 (~5-fold dilution) and 4 (~2.5-fold dilution) will evaluate using lower concentrations of QWO (CCH-aaes). Cohort 3 will evaluate using a shallower depth of injection. Taken together, this study will attempt to isolate the impact of each of these variables on bruising.

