	• Cohorts 7a and 7b: The proportion of participants within each cohort (ie, 7a and 7b) whose left buttock (investigational side) demonstrates at least 1-level lower score versus the right buttock (control side), on the IABSS, by corresponding treatment visit by buttock (first dose of QWO [CCH-aaes] on the investigational buttock with tranexamic acid vs the first dose of QWO [CCH-aaes] without tranexamic acid on the control side; second dose of QWO [CCH-aaes] on the investigational buttock vs second dose of QWO [CCH-aaes] on the control side; third dose of QWO [CCH-aaes] on the investigational side vs third dose of QWO [CCH-aaes] on the control side); and at each follow up visit thereafter.
To assess the level of aesthetic improvement of cellulite after treatment with QWO (CCH-aaes).	• The proportion of participants with an improved (+1 or better) score on the Investigator-Global Aesthetic Improvement Scale (I-GAIS) by treatment area at Days 22, 43, 64, 90, 135 and 180 Visits. The I-GAIS is a 7-point scale ranging from +3 (very much improved) to -3 (very much worse).
To assess the safety of QWO (CCH-aaes) for each study intervention in participants with cellulite.	• Proportion of participants reporting each treatment-emergent adverse events (TEAEs) throughout the study.
To assess the safety of QWO (CCH-aaes) for each study intervention in participants with cellulite.	• Proportion of participants reporting TEAEs of injection site reactions in the left buttock (investigational side) vs the right buttock (control side).
Exploratory	

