3.8.3. Investigator-Global Aesthetic Improvement Scale

At the time points indicated in the SoA (Table 3, Table 4, Table 5, and Table 6), the investigator will determine the degree of improvement of each buttock by comparing treated cellulite dimples from the Day 1 pre-treatment (Baseline) digital image of each buttock to the treated dimples observed in a live assessment (Table 9). I-GAIS will not be completed at Tx Visit 2 (Day 22) for the non-treated buttock for Cohorts 7a and 7b. Therefore, at Tx Visit 2 (Day 22) the I-GAIS will only be assessed for the investigational buttock (ie, left buttock) for Cohort 7a and only assessed for the control buttock (ie, right buttock) for Cohort 7b. For each buttock, the investigator will provide the rating from those below that best represents his/her answer.

Rating	Response Option	Description
+3	Very much improved	Optimal cosmetic result from treatment of the treated dimples
+2	Much improved	Marked improvement in the treated area appearance from before treatment, but not completely optimal
+1	Improved	Obvious improvement in the treated area appearance from before treatment, but additional treatment is indicated
0	No change	The treated area appearance is essentially the same as before treatment
-1	Worse	The treated area appearance is worse than before treatment
-2	Much worse	Marked worsening in appearance from the initial condition
-3	Very much worse	Obvious worsening in appearance from the initial condition

 Table 9:
 Investigator-Global Aesthetic Improvement Scale (I-GAIS)

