- Method of Analyses: The one-level I-GAIS responders will also be summarized by treatment area for each cohort using frequency, proportion and corresponding 95% CI based on the Clopper-Pearson method for one-level I-GAIS responders. The summary tables will be provided for Cohort 1-5 at Visit 6 (Day 22), Visit 11 (Day 43), Visit 16 (Day 90), Visit 17 (Day 135) and Visit 18 (Day 180). For Cohort 6 at Visit 7 (Day 43), Visit 12 (Day 90), Visit 13 (Day 135) and Visit 14 (Day 180) and for Cohort 7 at Visit 6 (Day 22), Visit 11 (Day 43), Visit 16 (Day 64), Visit 21 (Day 90), Visit 22 (Day 135) and Visit 23 (Day 180).
- Supportive analysis to secondary endpoint: Not applicable.

I-GAIS ratings will be summarized for Cohort 1-5 at Visit 6 (Day 22), Visit 11 (Day 43), Visit 16 (Day 90), Visit 17 (Day 135), and Visit 18 (Day 180). For Cohort 6 at Visit 7 (Day 43), Visit 12 (Day 90), Visit 13 (Day 135), and Visit 14 (Day 180) and for Cohort 7 at Visit 6 (Day 22), Visit 11 (Day 43), Visit 16 (Day 64), Visit 21 (Day 90), Visit 22 (Day 135) and Visit 23 (Day 180) by treatment area for each of the cohorts. The I-GAIS ratings by participant at each visit will be listed.

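### I-GAIS: the only result with a confidence interval is the per-side share rated +1 or better, so a drop from +3 to +1 is not counted, and no paired left-minus-right estimate is planned

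*SAP*

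**What the plan says.** The secondary objective in SAP section 2, Table 1, is "To assess the level of aesthetic improvement of cellulite after treatment with QWO (CCH-aaes"). The same table describes the instrument: "The I-GAIS is a 7-point scale ranging from +3 (very much improved) to -3 (very much worse"). Each buttock is rated separately.

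The endpoint uses one cut. Under SAP 4.5.2 a one-level responder for a buttock "is defined as any participant with an improved (+1, +2 or +3) score on the I-GAIS at an analysis visit". SAP 3.8.3, Table 9, gives the levels being merged quite different meanings. A +3 is "Optimal cosmetic result from treatment of the treated dimples"; a +1 is "Obvious improvement in the treated area appearance from before treatment, but additional treatment is indicated".

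The analysis is in SAP 7.6.2.3: "The one-level I-GAIS responders will also be summarized by treatment area for each cohort using frequency, proportion and corresponding 95% CI", by the Clopper-Pearson method. The estimand leaves its population-level summary measure undefined, and the last line reads "Supportive analysis to secondary endpoint: Not applicable". The same section also has the I-GAIS ratings themselves summarized by visit, treatment area and cohort, and listed by participant. Under SAP 6.1, discrete data are shown as frequencies and percentages.

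**The concern.** The objective asks how much improvement there was, and the responder asks only whether there was any. A participant rated +3 on the control side and +1 on the investigational side is a responder on both.

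This matters because in the schedules of assessments CR-PCSS and Hexsel scores are taken only at Screening and Day 1. I-GAIS is the one cellulite rating scheduled after treatment. In Cohorts 1, 5 and 6 the investigational side receives half the control-side dose, and Cohorts 2 to 4 change how the dose is delivered. For Cohort 6, Protocol 5.2 gives the purpose as "to determine whether there will be a decrease in bruising while experiencing an improvement in cellulite". If responder percentages on the two sides look alike because most buttocks reach +1, a reader could take that as benefit retained.

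The two scales are also handled differently. The IABSS responder in SAP 4.5.1 is a within-participant difference of one level. I-GAIS is summarized one side at a time, although Protocol 5.3 says that participants in Cohorts 1 to 6 serve as their own controls for all endpoints.

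**Working it through.** **The plan's own figure.** 7 × 30 = 210 enrolled, and 168/210 = 80% complete, or 168/7 = 24 per cohort on average. Neither document states an I-GAIS rate, effect size, test, margin or power, so there is no power figure to reproduce.

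**Limiting case, no assumptions needed.** Suppose all 30 control sides are +3 and all 30 investigational sides are +1. Both sides show 30/30 responders with the same Clopper-Pearson interval, 88.4% to 100% (24/24: 85.8% to 100%). The planned ratings table would show 100% at +3 against 100% at +1. The responder result misses the drop; the ratings table shows it, without an interval.

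**Assumptions for intermediate cases (mine).** Paired latent ratings are bivariate normal with SD 1 level, rounded to whole levels and clipped to −3 to +3. Correlation ρ is 0.4, 0.6 or 0.8. The control mean m is 1.0, 1.5 or 2.0, and the investigational side is 0.5 lower.

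Responder rate: P(rating ≥ +1) = P(latent ≥ 0.5) = Φ(m − 0.5).
- m = 1.0: control Φ(0.5) = 69%, investigational Φ(0) = 50%
- m = 1.5: control Φ(1.0) = 84%, investigational Φ(0.5) = 69%
- m = 2.0: control Φ(1.5) = 93%, investigational Φ(1.0) = 84%

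**Power**, two-sided 5%, 4,000 simulated cohorts per cell. Each entry is McNemar at the +1 cut versus signed-rank on the full rating, in %.

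| n | Control response | ρ = 0.4 | ρ = 0.6 | ρ = 0.8 |
|---|---|---|---|---|
| 30 | 69% | 38 v 61 | 44 v 76 | 61 v 94 |
| 30 | 84% | 30 v 61 | 36 v 74 | 48 v 94 |
| 30 | 93% | 22 v 58 | 24 v 74 | 27 v 92 |
| 24 | 69% | 29 v 51 | 37 v 66 | 50 v 86 |
| 24 | 84% | 25 v 49 | 31 v 64 | 39 v 86 |
| 24 | 93% | 16 v 48 | 19 v 62 | 19 v 83 |

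Relative loss = 1 − (cut power / full-scale power); for example 1 − 38/61 = 38%.
- n = 30: 35–42% at 69% response, 49–51% at 84%, 62–71% at 93%.
- n = 24: 42–44%, 49–55% and 67–77%.
- A separate run gave 58% as the lowest value at 93% response, so I quote about 35% to 44% at 69% and about 58% to 77% at 93%.

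**Size of the tests.** With no true loss, McNemar rejected in 0.6% to 4.9% of cohorts and signed-rank in 4.2% to 5.1%. McNemar is most conservative at 93% response, where few pairs differ in responder status. Part of the gap there comes from that conservatism, not only from the cut.

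**Ties.** Of pairs rated lower on the investigational side, 42% to 77% have the same responder status on both sides. Counting only pairs with both sides at +1 or better, it is 29% to 74%.

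**A second model as a check.** A latent normal was cut into levels 0 to +3, with ρ 0.5 or 0.8, a loss of 0.5 or 0.8 SD, n of 24 or 30, and mid-p McNemar. The direction was the same at every control response from 30% to 95%. The relative loss was 6% to 47% at 70% response and 55% to 94% at 95%.

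**Precision of the paired estimate.** The SD of the difference is about √(2(1 − ρ) + 1/6), where 1/6 allows for rounding: 1.17, 0.98 and 0.75 levels. The 95% half-width t·SD/√n at n = 30 (t = 2.045) is 0.44, 0.37 and 0.28 levels; at n = 24 (t = 2.069) it is 0.49, 0.41 and 0.32.

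**The case against.** The strongest reply is that the full scale is already reported. SAP 7.6.2.3 tabulates every rating by side and lists it by participant. A reader might infer that a cellulite cost would be hidden; the documents do not support that. What stands is narrower: the table shows two separate distributions, does not link a participant's two buttocks, and gives no interval for the difference.

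Second, a reader might infer that the plan throws away most of its power. No I-GAIS test is planned, so there is no planned power to lose. The figures above measure information discarded by the cut under assumed rates. More than half is lost only when most control sides already reach +1.

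Third, the +1 cut is the protocol's own endpoint (Protocol 4.1 and 10.3.1), and the SAP follows it. It is not a deviation. The Cohort 6 sentence in Protocol 5.2 asks for some improvement, which the cut does answer. That sentence covers Cohort 6 only; extending the interest in retained benefit to the other cohorts is my inference from the design.

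Fourth, the remedy is a paired contrast, so this may look like no more than the absence of pairing. The two overlap, but pairing the responder status alone would leave the ties described above.

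The exploratory efficacy text is largely blacked out. The statement that no paired I-GAIS analysis is planned applies to the readable text.

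**Conclusion.** The point holds in a limited form. The objective is the level of improvement, but the only I-GAIS interval is for a per-side proportion that treats +3 and +1 alike. No within-participant estimate on the full scale is planned in a self-controlled design. The mismatch itself needs no assumptions.

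Its size does. For a half-level loss and 30 pairs, power is about 22% to 61% at the cut against 58% to 94% on the full scale, over the correlations and response rates assumed. The relative loss grows with the control response rate, and at 93% part of it is test conservatism.

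This is an inexpensive improvement to a descriptive secondary endpoint in a Phase 2 study. It is not a flaw in the primary analysis.

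**What to change.** In SAP 7.6.2.3, keep the +1 responder proportion as the endpoint and replace the line "Supportive analysis to secondary endpoint: Not applicable" with a supportive analysis:

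- **Estimate.** For each cohort and I-GAIS visit, give the within-participant left-minus-right difference in rating as a mean or Hodges-Lehmann estimate with a 95% CI, plus counts rated lower, the same and higher on the left.
- **Tests.** Rest on the estimate and interval. Label any signed-rank p-value nominal and exploratory, because the analysis repeats over cohorts and visits.
- **Cohort 7.** Report 7a and 7b separately and compare at Days 135 and 180, or align by dose number. At Day 22 only one buttock is rated (SAP 3.8.3). At Day 90 the last scheduled doses were on Day 43 on one side and Day 64 on the other: 90 − 43 = 47 against 90 − 64 = 26 days, a 21-day difference.
- **Interpretation.** State that similar responder proportions alone do not show that cellulite benefit is retained, and make no retention claim from a non-significant difference. With half-widths of roughly 0.3 to 0.5 level and no margin defined, such a result would not exclude a meaningful loss.

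The cost is a short SAP edit and one extra table per cohort, with no new data, visits or participants. The downside is a summary less simple than a percentage, which is why the percentage stays.
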